Study Protocol

“Does Antrum Size Matter in Sleeve Gastrectomy?”

Study Protocol

“Does Antrum Size Matter in Sleeve Gastrectomy? ”

BACKGROUND

Laparoscopic sleeve gastrectomy (LSG) is currently the most frequent primary bariatric procedure performed worldwide. LSG is safe and effective in terms of excess weight loss. It is a powerful metabolic operation that activates significant hormonal pathways that lead to changes in eating behavior, glycemic control and intestinal functions. LSG can be a faster procedure for its technical aspects (any need for intestinal anastomosis, being limited to the stomach transection). The most frequent and sometimes dangerous complications are leaking, hemorrhage, splenic injury, stenosis and Gastroesophageal Reflux Disease (GERD)(1). Despite its established efficacy and safety, dispute still exists on optimal operative technique for LSG: bougie size, distance of resection margin from the pylorus, the shape of section at the gastroesophageal junction, staple line reinforcement and intraoperative leak testing are among the most controversial issues (2). Indeed, different Authors have adopted a resection distance from the pylorus between 2 and 6–7 cm with various reasons (3). In favor of resections more distant to the pylorus, Authors argue that it seems to improve gastric emptying, prevent distal stenosis and reduce intraluminal pressure, potentially leading to a lower incidence of fistula and/or reflux. On the other hand, resections close to the pylorus seems to reduce more the gastric distensibility and increase intragastric pressure, potentially leading to a better satiation with less oral intake (4, 5). However, only few studies have investigated the differences between these two approaches (3). Thus, the primary aim of this randomized monocentric study is to evaluate variations in percentage of excess weight loss (%EWL) at 1 and 2 years follow-up after LSG in subject with a gastric resection starting from 2 cm from the pylorus (wide antrectomy) compared to those with a gastric resection starting from 6 cm from the pylorus (small antrectomy). Secondary aim-points are represented by evaluation of differences in morbidity, mortality, tolerance to food, incidence of reflux symptoms and GERD Health-Related Quality-of-Life (GERD-HRQL) score between the two groups.

Material and Methods

This study was conducted from January 2015 to November 2017 in the Department of General and Emergency Surgery of "A. Rizzoli" Hospital in Lacco Ameno (Naples, Italy). All the procedures were

performed by the same surgeon. Morbid obesity was preoperatively diagnosed according to the International Federation for Surgery of Obesity (IFSO) guidelines (1). Patients were randomized into 2 groups: Group A (dissection starts at 2 cm proximally to the pylorus and continued along the greater curvature to the left crus) and Group B (dissection starts at 6 cm proximally to the pylorus and continued along the greater curvature to the left crus). Results were obtained at 1 and 2 years follow-up.

Pre-operative evaluation

Preoperative evaluation included anthropometric measurements (height in cm, weight in kg, Body Mass Index(BMI) in kg/m²), comorbidity evaluation [Glycated Hemoglobin(A1c), C-peptide, stimulated C-peptide, Electrocardiography (ECG), echocardiography, lower limbs US color-doppler study, thyroid function profile]. All patients were evaluated for the presence/absence of GERD before surgery. All patients were surveyed about the presence of heartburn and/or regurgitation with a specific questionnaire GERD HRQL questionnaire (6). Each of the 10 questions were rated from 0 (absence of symptoms) to 5 (severe symptoms) for a total score that may range from 0 to 50. Symptoms were defined as absent when patients reported a GERD-HRQL score of 0, mild from 1 to 15, moderate from 16 to 24, and severe from 25 to 50. Patients with GERD-HRQL score >16 was considered positive for GERD;(7). Atypical symptoms were also recorded. All patients underwent upper endoscopy (UE) after 20 days proton pump inhibitors (PPIs) or H2 blockers off, with Helicobacter Pylori(HP) test. When present, HP was eradicated according to Maastricht consensus(8). At UE, esophagitis presence was graded according Los Angeles Classification (9). PPI assumption and symptoms relief was also measured. In case of atypical symptoms and PPI refractoriness, pH-monitoring was indicated to confirm or exclude GERD diagnosis.

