2.2 Study Design

The study is designed as a randomized controlled trial. Primary outcome was the evaluation of %EWL between 2 groups. Secondary outcomes were evaluation of morbidity, mortality, incidence of reflux symptoms and Quality of Life score between the Groups.From January 2015 to November 2017, a series of 218 consecutive patients suffering from morbid obesity and scheduled for LSG were included; informed consent was obtained from each participant before surgery.

Inclusion criteria were morbid obesity defined as BMI 40 kg/m² and age between 25–50 years old. Obesity-related comorbidities included Type 2 Mellitus Diabetes (T2MD), hypertension, hyperlipidemia, bronchial asthma, osteoarthritis and degenerative joint disease.

Exclusion criteria

Patients with previous bariatric surgical procedures, endocrine disorders causing obesity (as hypothyroidism and Cushing disease), pregnancy or lactation, psychiatric illness, or recent diagnosis of malignancy, inflammatory bowel disease, Barrett's esophagus, and GERD with esophagitis scored as or greater than grade B, a large hiatal hernia (>3 cm) were excluded from the study. In case of absence or grade A esophagitis, GERD was also considered as severe with GERD-HRQL > 30 and when interfering with daily activities or inducing dietary restriction despite, also these were excluded.

One hundred-fifty patients were considered eligible and randomized in two Group (Group A n = 75, Group B n=75). All patients underwent elective laparoscopic LSG. In the case of conversion to open surgery, patients were excluded. Details of enrollment procedure are shown in Fig. 1.

Randomization

Participants were randomly assigned to one of the two groups using computer-generated permuted blocks (www.randomization.com). Outpatient clinic controls were done by surgeons/surgical residents/GP blinded for the groups. Patients were randomized into 2 groups based on the distance to pylorus of resection: Group A (n=75) at 2 cm, Group B(n=75) at 6 cm. Results were obtained at 1 and 2 years follow-up. The randomization scheme was generated using the web site Randomization.com (<http://www.randomization.com>).

Blinding Process

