2.6 Statistical Analysis

Statistical analysis was performed using Graphpad Quick Calcs (GraphPad version 6.04 for Windows, GraphPad Software, La Jolla California USA). Baseline comparisons were performed using chi-square tests and T-tests. Continuous variables are expressed as mean \pm standard deviation (SD). Differences between preoperative and postoperative parameters were compared by Wilcoxon paired rank test. For all tests, a two-sided $p < 0.05$ was considered statistically significant.

Sample size

THIS IS A CONTROLLED RANDOMIZED STUDY OF BINARY NON-INFERIORITY OUTCOME IN PARALLEL GROUPS. IF THERE IS TRULY NO DIFFERENCE BETWEEN THE STANDARD AND EXPERIMENTAL TREATMENT, THEN 138 PATIENTS ARE REQUIRED TO BE 90% SURE THAT THE LOWER LIMIT OF A ONE-SIDED 95% CONFIDENCE INTERVAL (OR EQUIVALENTLY A 90% TWO-SIDED CONFIDENCE INTERVAL) WILL BE ABOVE THE NON-INFERIORITY LIMIT OF -10. SAMPLE SIZE WAS CALCULATED WITH SEALED ENVELOPE LTD. 2012.

Appendix 2

Chief Investigator: [name], PhD – UOC Chirurgia Generale – Ospedale A. Rizzoli –

Lacco ameno napoli. [contact]; cellulare: [name].

Results summarized in the table:

Table 1 :Preoperative demographics data

Table 2: Weight, Body mass index, and the percentage of excess body weight loss and the Percentage Total Weight loss of the two groups at follow-up 3-6-12-24-months

Table 3: GERD Health-Related Quality-of-Life (GERD-HRQL) Score preoperative and postoperative scores follow-up 3-6-12-24 months

Table 4: Endoscopy Preoperative and at 1 and 2 years follow-up into two Groups

Table 1 Preoperative demographics data

Patients	Total	Group A (n=75)	Group B(n=75)
Age	33.6 ± 14	32.2 ± 8	34.2 ± 9
Male	39%	35%	38%
Female	61%	63%	62%
Height	151.2 ± 22	150.1 ± 23	152.8 ± 33
Weight kg	121.9 ± 21.7	124.5 ± 26.7	125.3 ± 23.5
BMI	44.23 ± 6.32	43 ± 8 (40–57)	44 ± 4(40–55)
ASA(I-II)(%)	65%	64%	66%
ASA(III-IV)(%)	35%	36%	34%
T2MD(%)	12(8.%)	7(9.3%)	5(6.6%)
Chronic obstructive pulmonary disease(%)	7(4.6%)	2(2.6%)	3(4%)
Heart Ischemia	1	0	0
Hypertension(%)	95(63%)	55(73.3%)	40(53.4%)

BMI body mass index, %EWL percentage excess weight loss, %TWL percentage total weight loss, Type 2 Mellitus Diabetes (T2MD)

Table 2: Weight, Body mass index, and the percentage of excess body weight loss and the Percentage Total Weight loss of the two groups at follow-up

Patients	3 months follow-up		p	6 months follow-up		p	12 months follow-up		p	24 months follow-up		p
	145/150			141/150			136/150			131/150		

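### The primary aim covers %EWL at both 1 and 2 years, each at two-sided 0.05, and no rule says which time point, or whether both, must succeed

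*Combined protocol and SAP*

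**What the plan says.** The Background sets the primary aim as to "evaluate variations in percentage of excess weight loss (%EWL) at 1 and 2 years follow-up after LSG". Section 2.2 restates it without a time point: "Primary outcome was the evaluation of %EWL between 2 groups". Material and Methods, and again the Randomization paragraph, say only "Results were obtained at 1 and 2 years follow-up".

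Section 2.6 gives one significance rule: "For all tests, a two-sided $p < 0.05$ was considered statistically significant". Its only between-group tests are tied to baseline ("Baseline comparisons were performed using chi-square tests and T-tests"), and a paired Wilcoxon test is named for pre- versus postoperative change. No test is named for comparing %EWL between arms at follow-up.

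The Sample size paragraph uses a different frame. It says "THIS IS A CONTROLLED RANDOMIZED STUDY OF BINARY NON-INFERIORITY OUTCOME IN PARALLEL GROUPS", and that "138 PATIENTS ARE REQUIRED TO BE 90% SURE THAT THE LOWER LIMIT OF A ONE-SIDED 95% CONFIDENCE INTERVAL" "WILL BE ABOVE THE NON-INFERIORITY LIMIT OF -10". It describes a single comparison and names no time point.

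Table 2 prints P<0.05 for %EWL at 12 months and p>0.05 at 24 months.

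**The concern.** Two time points share the primary aim, and the plan does not say how they combine. It does not choose one, rank them, divide alpha between them or require both. Under the general 0.05 rule, a significant result at either time could be presented as the primary finding, and the choice could be made after both results are known. The 5% then no longer describes the chance of a false primary claim.

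The gap has practical weight here because the two verdicts printed in Table 2 differ. As printed, the table could be cited for a weight-loss advantage of the 2 cm resection at 12 months or for no difference at 24 months. The plan would not rule out calling either one the primary result.

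**Working it through.** **1. The plan's own figure (138).** The Sample size paragraph gives 90% power, one-sided 5%, true difference 0 and a limit of -10. It gives neither an SD (needed for a continuous outcome) nor a success rate (needed for a binary one), so 138 cannot be reproduced from stated inputs. Back-solving, with (1.645 + 1.282)² = 8.57:
- Continuous: n per arm = 2 × SD² × 8.57 / 10². SD 20 gives 68.5, rounded up to 69, total 138.
- Binary, 10-point limit: n per arm = 2 × p(1 − p) × 8.57 / 0.10². A total of 138 needs p of about 0.958; p = 0.90 gives 310.

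Either way, the figure covers one comparison at one unnamed time.

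**2. False-claim rate if either time point may win.** Each test is two-sided at 0.05 (critical value 1.96). The chance of at least one false rejection is 1 − P(|Z₁| < 1.96 and |Z₂| < 1.96), with Z₁ and Z₂ bivariate normal. The documents give no 12–24-month correlation, so a range is assumed.

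| Correlation (assumed) | Either time wins |
|---|---|
| 0 | 1 − 0.95² = 9.75% |
| 0.5 | 9.1% |
| 0.7 | 8.3% |
| 0.8 | 7.8% |
| 0.9 | 7.0% |
| 0.95 | 6.5% |

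The rate approaches 5% only as the correlation approaches 1. If both times must succeed, it cannot exceed 5%.

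**3. Table 2 verdicts (Group A versus Group B, %EWL).**
- 12 months: 63.7 ± 14.1 (n=67) versus 59.6 ± 12.5 (n=69). Difference 4.1; SE = √(14.1²/67 + 12.5²/69) = 2.29; t about 1.80; two-sided p = 0.075, pooled or Welch. Taking the most favourable rounding of every tabulated value, p = 0.067. The printed P<0.05 is not reproduced.
- 24 months: 62.8 ± 13.1 (n=65) versus 61.6 ± 10.5 (n=66). Difference 1.2; SE = √(13.1²/65 + 10.5²/66) = 2.08; t about 0.58; two-sided p = 0.56. This agrees with the printed p>0.05.

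**4. The non-inferiority frame, if -10 means %EWL points.** Lower limit of the two-sided 90% interval = difference − 1.645 × SE, on available cases (136 and 131 of 150).

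| | 12 months | 24 months |
|---|---|---|
| B minus A | −4.1 − 1.645 × 2.287 = −7.9 | −1.2 − 1.645 × 2.076 = −4.6 |
| A minus B | 4.1 − 1.645 × 2.287 = +0.3 | 1.2 − 1.645 × 2.076 = −2.2 |

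All four lie above -10.

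**The case against.** Three objections have force.

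First, no section states an either-wins rule, and no correlation is given. A reader might infer that the false-claim rate simply is 8–9%. That band needs both an either-wins reading and a correlation of about 0.53 to 0.77. This objection stands, so the rate is given here only as a conditional range. The gap itself remains: the plan does not exclude an either-wins reading.

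Second, a reader might infer from Table 2 that the primary conclusion flips between 12 and 24 months because multiplicity was not controlled. The tabulated data do not show that. By t-test neither time point reaches 0.05 even without adjustment. The printed difference in verdicts could come from an unstated test, such as a rank test on individual data, from a one-sided test (0.075 / 2 gives about 0.037, against the plan's two-sided rule), or from a reporting error. The documents do not settle which.

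Third, the trial was sized for non-inferiority. If the limit is in %EWL points, both times pass in either direction, so under that frame the conclusion does not depend on which time is chosen. This also stands, but only conditionally: the paragraph calls the outcome binary, gives the limit no unit and does not identify the experimental arm. The two-sided 0.05 rule remains the only significance rule that the plan states for its tests.

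**Conclusion.** The omission is real and should be corrected. Two primary time points fall under a single 0.05 rule, with nothing on how they combine. The consequence is conditional: above 5% and at most 9.75% if either time may support the claim, and no inflation if both must succeed.

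The 12-month verdict in Table 2 should not be relied on until the between-arm test and exact p are given. The recalculation assumes a t-test on the tabulated available-case summaries; individual data or another test could give a different value. Neither an unconditional 8–9% error rate nor a conclusion reversed by multiplicity is supported.

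**What to change.** State one decision rule in section 2.6 and label it post hoc. Results are already printed, so no rule written now can count as pre-specified.

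- **Superiority:** use a fixed sequence, for example 24 months first at two-sided 0.05 and 12 months only if 24 months succeeds, or require both times. Nothing in the documents ranks 24 months above 12, so the order needs a stated reason. On the recalculated p-values no superiority claim would follow under either rule.
- **Non-inferiority:** require the lower limit to be above -10 at both times; no alpha adjustment is needed when both must pass. First reconcile the binary wording with the continuous %EWL outcome, give the unit of -10 and say which arm is experimental. If -10 means %EWL points, non-inferiority holds at both times on available cases.
- **Reporting:** name the between-arm test for %EWL and give exact p-values and confidence intervals at 12 and 24 months. Correct or explain the 12-month entry in Table 2.

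The cost is a few sentences in 2.6 and a check of one table entry. The small downside is that 12 months alone could no longer support a superiority claim.

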	Group A (n=72)	Group B(n=73)	p>0.05	Group A(n=70)	Group B(n=71)	P<0.05	Group A(n=67)	Group B(n=69)	p	Group A(n=65)	Group B(n=66)	p>0.05
BMI	30.9 ± 5.32	34.7 ± 4.18	P<0.05	26.13 ± 7.32	31.06 ± 3.12	P<0.05	24.2 ± 3.4	27.5 ± 4.3	P<0.05	25.2 ± 4.4	26.2 ± 3.3	p>0.05
EBWL%	40.9 ± 8.1	31.60 ± 8.7	P<0.05	54.1 ± 11.3	48.20 ± 12.5	P<0.05	63.7 ± 14.1	59.6 ± 12.5	P<0.05	62.8 ± 13.1	61.6 ± 10.5	p>0.05

Results

Table 3 GERD Health-Related Quality-of-Life (GERD-HRQL) Score preoperative and postoperative scores

Patients	Preoperative 150/150		3 months follow-up 145/150		p >0.05	6 months follow-up 141/150		P <0.05	12 months follow-up 136/150		P <0.05	24 months follow-up 131/150		p >0.05
	Group A (n=75)	Group B (n=75)	Group A (n=72)	Group B (n=73)		Group A (n=70)	Group B (n=71)		Group A (n=67)	Group B (n=69)		Group A (n=65)	Group B (n=66)	
GERD HRQL Score<15			38(52.7%)	57(78%)	P <0.05	36(51.4%)	56(78.8%)	P <0.05	47(70.4%)	55(79.7%)	P <0.05	49(75.3%)	55(83.3%)	P <0.05
GERD HRQL Score >16<30	7(9.3%)	9(12%)	29(40%)	15(20.5%)	P <0.05	30(42.8%)	14(19.7%)	P <0.05	16(23.8%)	13(18.8%)	P >0.05	14(21.5%)	10(15.1%)	P >0.05
GERD HRQL Score >31	-	-	5(6.9%)	1(1.3%)	P <0.05	4(5.7%)	1(1.4%)	P <0.05	4(5.9%)	1(1.4%)	P <0.05	1(1.5%)	0	P <0.05
Significant Vomit	-	-	11(15,3%)	3(4.1%)	P <0.05	6(8.6%)	2(2.8%)	P <0.05	6(8.9%)	2(2.9%)	P <0.05	2(3.1%)	1(1.5%)	P <0.05
Intolerance to food	-	-	2(2.7%)	0	P <0.05	1(1.4%)	0	p >0.05	0	0	p >0.05	0	0	p >0.05

Table 4: Endoscopy Preoperative and at 1 and 2 years follow-up into two Groups

	Preoperative Patients 150		1 year follow-up Patients 108/150(72%)		2 years follow-up Patients 105/150(70%)	
	Group A 75	Group B 75	Group A 53	Group B 55	Group A 52	Group B 53
Esophagitis						
A	4(5.3%)	5(6.7%)	9(16.9%)	7(12.7%)	5(9.6%)	5(9.4%)
B	-	-	11(20.7%)	5(9%)	9(17.3%)	3(5.6%)
C	-	-	2(3.8%)	0	1(1.9%)	0
D	-	-				
Esophageal biopsy						
Metaplasia	-	-	0	0	0	0
Helicobacter Pylori	9(12%)	7(9.3%)				
Hiatal Hernia< 5 cm	1(1.3%)	2(2.7%)	-	-	-	-

Figure 1 Diagram of Patients eliability

Flow Diagram

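### Table 3 does not use the plan's own GERD-HRQL bands, leaves one patient per arm unplaced at 24 months, and prints 12- and 24-month p values that its counts do not support

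*Combined protocol and SAP*

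**What the plan says.** The Pre-operative evaluation section scores GERD-HRQL from 0 to 50. A score of 0 is absent, and the rest is graded "mild from 1 to 15, moderate from 16 to 24, and severe from 25 to 50". The same section sets a separate cut: "Patients with GERD-HRQL score >16 was considered positive for GERD".

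Section 2.2, under Exclusion criteria, attaches the word severe to another threshold: "GERD was also considered as severe with GERD-HRQL > 30", combined with interference with daily activities or dietary restriction.

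Section 2.5 lists the GERD score among the secondary endpoints. Section 2.6 names tests for baseline comparisons and for change from before to after surgery. It names none for comparing the arms on GERD-HRQL categories at follow-up, and says nothing on multiplicity.

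Table 3 has three score rows, "GERD HRQL Score<15", "GERD HRQL Score >16<30" and "GERD HRQL Score >31", each with its own p value at 3, 6, 12 and 24 months. Its last visit is headed "24 months follow-up 131/150", with 65 patients in Group A (2 cm) and 66 in Group B (6 cm).

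**The concern.** The cut at 25 appears nowhere in Table 3, absent and mild are merged, and, read literally, scores of 15, 16, 30 and 31 have no row. The middle row mixes the plan's moderate patients (17-24) with some of its severe ones (25-29). The plan's severity grading therefore cannot be read from the results.

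The three rows are also parts of one variable. A separate p value for each gives 12 linked tests of one score over four visits, and 10 of them are printed as P<0.05. Reflux is one of the arguments in the Background for choosing between the two resection distances. A reader of Table 3 would conclude that the arms still differ at 12 and 24 months, so it matters whether the counts show that.

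**Working it through.** **Step 1. Do the rows add up to the stated denominators?** Inputs are the Table 3 counts (below 15 + middle row + above 31).

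| Visit | Group A | n | Group B | n |
|---|---|---|---|---|
| 3 mo | 38+29+5 = 72 | 72 | 57+15+1 = 73 | 73 |
| 6 mo | 36+30+4 = 70 | 70 | 56+14+1 = 71 | 71 |
| 12 mo | 47+16+4 = 67 | 67 | 55+13+1 = 69 | 69 |
| 24 mo | 49+14+1 = 64 | 65 | 55+10+0 = 65 | 66 |

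The denominators reproduce at 3, 6 and 12 months. At 24 months each arm is one short. The percentages there use 65 and 66, so the rows add to about 98.5% in each arm.

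**Step 2. Bound the plan's severe category (25-50).** The lower bound is the above-31 row alone. The upper bound adds the whole middle row and any unplaced patient.

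- 3 months: A 5 to 5+29 = 34 of 72; B 1 to 1+15 = 16 of 73.
- 12 months: A 4 to 4+16 = 20 of 67; B 1 to 1+13 = 14 of 69.
- 24 months: A 1 to 1+14+1 = 16 of 65 (1.5% to 24.6%); B 0 to 0+10+1 = 11 of 66 (0% to 16.7%).

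**Step 3. Derive GERD-positive (above 16).** This cut coincides with a row boundary, so the count is the middle row plus the top row. Arms are compared by two-sided Fisher exact test.

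| Visit | Group A | Group B | Difference (points) | p |
|---|---|---|---|---|
| 3 mo | 34/72 (47.2%) | 16/73 (21.9%) | 25.3 | 0.0016 |
| 6 mo | 34/70 (48.6%) | 15/71 (21.1%) | 27.4 | 0.0008 |
| 12 mo | 20/67 (29.9%) | 14/69 (20.3%) | 9.6 | 0.24 |
| 24 mo | 15/65 (23.1%) | 10/66 (15.2%) | 7.9 | 0.27 |

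At 24 months the two unplaced patients may or may not be positive. The four possible placements give p = 0.27 (15 v 10), 0.39 (15 v 11), 0.19 (16 v 10) and 0.29 (16 v 11).

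An approximate 95% interval for the late differences is the difference ± 1.96 × √(pA(1−pA)/nA + pB(1−pB)/nB). At 12 months this is 9.6 ± 1.96 × 7.40 = −4.9 to 24.1 points. At 24 months it is 7.9 ± 1.96 × 6.84 = −5.5 to 21.3 points.

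**Step 4. Compare the printed row p values with the counts.** Fisher p, with the printed entry in brackets:

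| Row | 3 mo | 6 mo | 12 mo | 24 mo |
|---|---|---|---|---|
| below 15 | 0.0016 (<0.05) | 0.0008 (<0.05) | 0.24 (<0.05) | 0.29 (<0.05) |
| middle | 0.012 (<0.05) | 0.0037 (<0.05) | 0.53 (>0.05) | 0.37 (>0.05) |
| above 31 | 0.12 (<0.05) | 0.21 (<0.05) | 0.21 (<0.05) | 0.50 (<0.05) |

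Ten of 12 cells are printed as P<0.05, and the counts support four. An uncorrected chi-square test gives the same four; its 12- and 24-month values are 0.20 and 0.26 for the bottom row, and 0.16 and 0.31 for the top row. At 12 months the bottom row is the exact complement of GERD-positive, so the two must share one p value, here 0.24.

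**The case against.** Several stronger readings are tempting, and the documents do not support them.

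- *GERD-positive cannot be read from Table 3.* It can, by adding two rows. With literal labels this is exact at 3, 6 and 12 months and within one patient per arm at 24 months. What is missing is a line reporting it.
- *The cuts were picked once the grading had been fixed, to multiply claims.* Nothing dates the cuts. The exclusion threshold of above 30 is an ordinary possible source for the top row, which follows it except at a score of 31.
- *Table 3 misstates severe GERD.* No row is labelled severe, and there is no results narrative that makes a severity claim.
- *The unplaced patients fell into gaps between the bands.* At the three earlier visits the rows account for everyone, so either nobody scored 15, 16, 30 or 31, or the labels are loose. A missing questionnaire or a counting error would explain 24 months equally well.

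It can also be said that grading symptoms and declaring GERD are separate acts, so a score of 16 may be moderate without being positive. That is coherent, but it is an untidy boundary that needs a sentence of explanation. Finally, this is a secondary endpoint, the middle row is already printed as P>0.05 at 12 and 24 months, and the heading of the 24-month column carries a p>0.05 entry tied to no row. All of this limits the consequence. It does not account for the P<0.05 entries in the other two rows.

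**Conclusion.** The point holds as a reporting and analysis fault in a secondary endpoint. Table 3 departs from the plan's bands, so severe (25-50) is known only within wide limits. One patient per arm at 24 months is unaccounted for. Severe carries two meanings in the documents. The late P<0.05 entries in the bottom and top rows do not follow from the printed counts.

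On one comparison per visit, the arms differ in GERD-positive at 3 and 6 months, by about 25 and 27 points, and that finding stands. At 12 and 24 months a difference is not shown, wherever the unplaced patients belong. A reader should not infer equal reflux at those visits either, because the intervals reach above 20 points.

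These results assume that the row labels are literal. If they mean up to 15, 16 to 30, and 31 or more, patients scoring exactly 16 would be counted as positive here. They also assume that the counts, rather than the printed p values, are correct, and they concern attenders only. The primary outcome, %EWL, is not affected.

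**What to change.** 1. Re-tabulate GERD-HRQL by arm and visit from the scores already held, on the exhaustive, non-overlapping bands of the Pre-operative evaluation section (0, 1-15, 16-24, 25-50), with GERD-positive (above 16) as its own line.
2. Account for the unplaced patient in each arm at 24 months, and state the reason.
3. Replace the row-by-row p values with one named between-group comparison of GERD-positive per visit, supported by an analysis of the 0-50 score.
4. Limit any reflux claim to what this supports: on the present counts, a difference at 3 and 6 months that is not shown at 12 or 24 months.
5. Reconcile the Pre-operative evaluation section with the Exclusion criteria on the meaning of severe, and explain 16 against above 16. Which threshold is right is for the investigators to decide.

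The cost is a re-tabulation with no new data. The price is fewer cells marked significant.
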